6.5.4.4 Immune-related adverse events

AEs associated with pembrolizumab exposure may represent an immunologic etiology. These immune-related AEs (irAEs) may occur shortly after the first dose or several months after the last dose of pembrolizumab treatment and may affect more than one body system simultaneously. IrAEs are thought to be caused by unrestrained cellular immune responses directed at the normal host tissues. Therefore, early recognition and initiation of treatment is critical to reduce complications. Based on existing pembrolizumab clinical study data, most irAEs were reversible and could be managed with interruptions of pembrolizumab, administration of corticosteroids and/or other supportive care.

Investigators must be extremely vigilant and be ready to intervene early in the management of irAEs because the onset of symptoms of irAEs (eg, pneumonitis) may be subtle. For suspected irAEs, adequate evaluation should be performed to confirm etiology or exclude neoplastic, infectious, metabolic, toxin, or other etiologic causes. Additional procedures or tests such as bronchoscopy, endoscopy, skin biopsy may be included as part of the evaluation. Based on the severity of irAEs, withhold or permanently discontinue pembrolizumab and/or SAR444245 and administer corticosteroids.

SAR444245 may increase the incidence and severity of these events.

Dose modification and toxicity management guidelines for irAEs are provided in [Table 9](#). Of note, when study interventions are administered in combination, if the AE is considered immune-related, both drugs in the combination should be held according to recommended dose modifications. If a participant experiences several irAEs, the most conservative recommendation should be followed.

The CTCAE V5.0 must be used to grade the severity of AEs.

When pembrolizumab can be restarted, it should be administered at the initial planned dose and schedule as no modification is allowed:

- If the toxicity does not resolve or the criteria for resuming treatment are not met, the participant must be discontinued from all study drugs.
- If the toxicities do resolve and conditions are aligned with what is defined in [Table 9](#), the combination of SAR444245 and pembrolizumab or cetuximab may be restarted at the discretion of the investigator. In these cases where the toxicity is attributed to the combination or to SAR444245 alone, re-initiation of pembrolizumab as a monotherapy may be considered after communication with the Sponsor.

Table 9 - Dose modification and toxicity management guidelines for immune-related AEs associated with pembrolizumab and SAR444245

General instructions:

1. Severe and life-threatening irAEs should be treated with IV corticosteroids followed by oral steroids. Other immunosuppressive treatment should begin if the irAEs are not controlled by corticosteroids.
2. Pembrolizumab and SAR444245 must be permanently discontinued if the irAE does not resolve or the corticosteroid dose is not \leq 10 mg/day within 12 weeks of the last pembrolizumab treatment.
3. The corticosteroid taper should begin when the irAE is \leq Grade 1 and continue at least 4 weeks.
4. If pembrolizumab and SAR444245 have been withheld, pembrolizumab and SAR444245 may be resumed after the irAE decreased to \leq Grade 1 after corticosteroid taper.

irAEs	Toxicity grade (CTCAE V5.0)	Action with pembrolizumab and SAR444245	Corticosteroid and/or other therapies	Monitoring and follow-up
Pneumonitis	Grade 2	Withhold ^a	Administer corticosteroids (initial dose of 1-2 mg/kg prednisone or equivalent) followed by taper.	Monitor participants for signs and symptoms of pneumonitis.
	Recurrent Grade 2, Grade 3 or 4	Permanently discontinue ^b	Add prophylactic antibiotics for opportunistic infections.	Evaluate participants with suspected pneumonitis with radiographic imaging and initiate corticosteroid treatment.
Diarrhea/Colitis	Grade 2 or 3	Withhold ^a	Administer corticosteroids (initial dose of 1-2 mg/kg prednisone or equivalent) followed by taper.	Monitor participants for signs and symptoms of enterocolitis (ie, diarrhea, abdominal pain, blood or mucus in stool with or without fever) and of bowel

irAEs	Toxicity grade (CTCAE V5.0)	Action with pembrolizumab and SAR444245	Corticosteroid and/or other therapies	Monitoring and follow-up
	Recurrent Grade 3 or Grade 4	Permanently discontinue ^b		perforation (ie, peritoneal signs and ileus). Participants with ≥Grade 2 diarrhea suspecting colitis should consider GI consultation and performing endoscopy to rule out colitis. Participants with diarrhea/colitis should be advised to drink liberal quantities of clear fluids. If sufficient oral fluid intake is not feasible, fluid and electrolytes should be substituted via IV infusion.
AST or ALT elevation or Increased Bilirubin	Grade 2 ^c	Withhold ^a	Administer corticosteroids (initial dose of 0.5-1 mg/kg prednisone or equivalent) followed by taper.	Monitor with liver function tests (consider weekly or more frequently until liver enzyme value returns to baseline or is stable).
	Grade 3 ^d or 4 ^e	Permanently discontinue ^b	Administer corticosteroids (initial dose of 1-2 mg/kg prednisone or equivalent) followed by taper.	
Type 1 Diabetes Mellitus (T1DM) or Hyperglycemia	New onset T1DM or Grade 3 or 4 hyperglycemia associated with evidence of β-cell failure	Withhold ^{a,f}	Initiate insulin replacement therapy for participants with T1DM. Administer anti-hyperglycemic in participants with hyperglycemia.	Monitor participants for hyperglycemia or other signs and symptoms of diabetes.
Hypophysitis	Grade 2	Withhold ^a	Administer corticosteroids and initiate hormonal replacements as clinically indicated.	Monitor for signs and symptoms of hypophysitis (including hypopituitarism and adrenal insufficiency).
	Grade 3 or 4	Withhold ^a or permanently discontinue ^{b,f}		
Hyperthyroidism	Grade 2	Continue	Treat with non-selective beta-blockers (eg, propranolol) or thionamides as appropriate.	Monitor for signs and symptoms of thyroid disorders.
	Grade 3 or 4	Withhold ^a or permanently discontinue ^{b,f}		

irAEs	Toxicity grade (CTCAE V5.0)	Action with pembrolizumab and SAR444245	Corticosteroid and/or other therapies	Monitoring and follow-up
Hypothyroidism	Grade 2, 3, or 4	Continue	Initiate thyroid replacement hormones (eg, levothyroxine or liothyronine) per standard of care.	Monitor for signs and symptoms of thyroid disorders.
Nephritis: grading according to increased creatinine or acute kidney injury	Grade 2	Withhold ^a	Administer corticosteroids (prednisone 1-2 mg/kg or equivalent) followed by taper.	Monitor changes of renal function.
	Grade 3 or 4	Permanently discontinue ^b		
Neurological Toxicities	Grade 2	Withhold ^a	Based on severity of AE administer corticosteroids	Ensure adequate evaluation to confirm etiology and/or exclude other causes
	Grade 3 or 4	Permanently discontinue ^b		
Myocarditis	Grade 2, 3 or 4	Permanently discontinue ^b	Based on severity of AE administer corticosteroids.	Ensure adequate evaluation to confirm etiology and/or exclude other causes.
Exfoliative Dermatologic Conditions	Suspected SJS, TEN, or DRESS	Withhold ^a	Based on severity of AE administer corticosteroids	Ensure adequate evaluation to confirm etiology or exclude other causes
	Confirmed SJS, TEN, or DRESS	Permanently discontinue ^b		
	Persistent Grade 2	Withhold ^a	Based on severity of AE administer corticosteroids.	Ensure adequate evaluation to confirm etiology or exclude other causes.
All Other immune-related AEs	Grade 3	Withhold ^a or discontinue based on the event ^g		
	Recurrent Grade 3 or Grade 4	Permanently discontinue ^b		

a SAR444245 to be withheld plus pembrolizumab to be withheld corresponds to "cycle delay".

b Permanently discontinuation of full study treatment.

c AST/ALT: >3.0 - 5.0 x ULN if baseline normal; >3.0 - 5.0 x baseline, if baseline abnormal; bilirubin:>1.5 - 3.0 x ULN if baseline normal; >1.5 - 3.0 x baseline if baseline abnormal.

d AST/ALT: >5.0 to 20.0 x ULN, if baseline normal; >5.0 - 20.0 x baseline, if baseline abnormal; bilirubin:>3.0 - 10.0 x ULN if baseline normal; >3.0 - 10.0 x baseline if baseline abnormal.

e AST/ALT: >20.0 x ULN, if baseline normal; >20.0 x baseline, if baseline abnormal; bilirubin: >10.0 x ULN if baseline normal; >10.0 x baseline if baseline abnormal.

f The decision to withhold or permanently discontinue pembrolizumab and/or SAR444245 is at the discretion of the investigator or treating physician. If control achieved or ≤Grade 2, pembrolizumab and SAR444245 may be resumed.

g Events that require discontinuation include but are not limited to: encephalitis and other clinically important irAEs (eg. vasculitis and sclerosing cholangitis).

AE(s)=adverse event(s); ALT= alanine aminotransferase; AST=aspartate aminotransferase; CTCAE=Common Terminology Criteria for Adverse Events; DRESS=Drug Rash with Eosinophilia and Systemic Symptom; GI=gastrointestinal; ir=immune related; IV=intravenous; SJS=Stevens-Johnson Syndrome; T1DM=type 1 diabetes mellitus; TEN=Toxic Epidermal Necrolysis; ULN=upper limit of normal.

Note: Non-irAE will be managed as appropriate, following clinical practice recommendations.

6.5.4.5 Immune Cell-Associated Neurotoxicity Syndrome (ICANS)

Immune cell-associated neurotoxicity syndrome (ICANS) is a neuropsychiatric syndrome which is frequently associated with CRS; however, it is specifically excluded from the definition of CRS and can occur during the course of CRS, after its resolution, or independently from CRS. Clinical findings can be progressive and may include aphasia, altered level of consciousness, impairment of cognitive skills, motor weakness, seizure, and cerebral edema. Severity is evaluated using the ASTCT Consensus grading scale, with ICE score for encephalopathy assessment (Section 10.11 of the master protocol). Recommendations for ICANS management mainly include the use of steroids, whereas tocilizumab should only be used in the context of CRS, as outlined in [Table 10](#). The proposed management should be considered only as recommendations and in light of recommendations from site specialist.

Table 10 - Guidelines for the management of immune Cell-Associated Neurotoxicity Syndrome (ICANS)

Event severity (ASTCT Consensus Grading criteria)	Recommended SAR444245 dose modification and supportive care guidelines
Mild Grade 1 ICE score 7-9. Awakens spontaneously	No intervention required other than close clinical monitoring.
Moderate Grade 2 ICE score 3-6. Awakens to voice.	SAR444245^a should be delayed. Treatment with IV corticosteroids should be initiated as needed. SAR444245 may be resumed only after participant recovery or improvement to Grade 1 after corticosteroid taper. Consideration for reduction of SAR444245 dose to █ µg/kg as per Investigator with Sponsor consultation.
Severe or Life-threatening Grade 3 ICE score 0-2. Awakens only to tactile stimulus. Any clinical seizure focal or generalized that resolves rapidly or nonconvulsive seizures on EEG that resolve with intervention.	If Grade 3 ICANS, SAR444245 should be delayed. When symptoms have resolved or improved to Grade 1 after corticosteroid taper, SAR444245 can be either restarted at █ µg/kg or permanently discontinued, as clinically indicated, and upon discussions between the Investigator and Sponsor.
Grade 4 ICE score: 0 (participant is unarousable and unable to perform ICE). Participant is unarousable or requires vigorous or repetitive tactile stimuli to arouse. Stupor or coma. Life-threatening prolonged seizure (>5 min): or Repetitive clinical or electrical seizures without return to baseline in between. Deep focal motor weakness such as hemiparesis or paraparesis. Diffuse cerebral edema on neuroimaging; decerebrate or decorticate posturing; or cranial nerve VI palsy; or papilledema; or Cushing's triad.	If Grade 4 ICANS, both SAR444245 and pembrolizumab should be permanently discontinued. Treatment with IV corticosteroids should be initiated. Concomitant CRS may require tocilizumab and should be handled as described in Table 8 in Section 6.5.4.3 . Corticosteroids can then be administered IV or orally every 8 hours for up to 3 days, then tapered over 4 days. For both Grade 3 and Grade 4 ICANS If there is no clinical improvement within 24 to 72 hours, then re-evaluation for other contributing conditions should be done. Administration of IV Tocilizumab at 8 mg/kg (for participants weighing ≥30 kg, total dose should not exceed 800 mg) should be considered, and steroids should be administered concurrently and repeated as previously mentioned for CRS. Neurologist and other relevant clinical specialists should be involved whenever indicated.

^a Information for preparation and storage of SAR444245 is provided in the pharmacy manual

Abbreviations: ASTCT=American Society for Transplantation and Cellular Therapy; CRS= cytokine release syndrome; ICANS= Immune effector cell associated neurotoxicity syndrome; ICE= Immune Effector Cell-Associated Encephalopathy; IV = Intravenous.

6.5.4.6 Vascular Leak Syndrome (VLS)

Vascular leak syndrome is a disorder characterized by leakage of intravascular fluids into the extravascular space and can lead to generalized edema and multiple organ failure. This syndrome is observed in patients who demonstrate a state of generalized leaky capillaries following shock syndromes, low-flow states, ischemia-reperfusion injuries, toxemias, medications, or poisoning. In various human diseases, an increase in capillary permeability to proteins leads to the loss of protein-rich fluid from the intravascular to the interstitial space manifested by any of the following **clinical presentations: diffuse pitting edema, exudative serous cavity effusions, noncardiogenic pulmonary edema, hypotension, and, in some cases, hypovolemic shock with multiple-organ failure**. Fluid management is the cornerstone of VLS management; it is a balance between maintaining the intravascular volume to ensure organ perfusion to prevent organ failure, while avoiding volume overload. The management of VLS according to severity grading is described in [Table 11](#). These guidelines are not comprehensive and the Investigator should exercise clinical judgment based on the symptoms and condition of the individual participant and refer to current guidelines to the topic [\(38\)](#).

Table 11 - Guidelines for the management of Vascular Leak Syndrome (VLS)

Event severity (NCI-CTCAE V5.0)	Recommended SAR444245 dose modification and supportive care guidelines
Mild	No intervention required other than clinical monitoring.
Grade 1	
Asymptomatic	
Moderate	SAR444245 should be delayed. Upon resolution of VLS or improvement to
Grade 2	Grade 1, SAR444245 ^a can be resumed at the reduced dose of █ µg/kg.
Symptomatic; medical intervention indicated	The initial strategy is to administer boluses of crystalloids with a goal of providing the minimum effective volume that optimizes blood pressure together with a fluid-restrictive strategy is advocated to limit interstitial fluid volume expansion.
Severe or Life-threatening	If Grade 3 or Grade 4 VLS, SAR444245 should be permanently discontinued.
Grade 3:	In participants with severe shock, blood pressure may be only partially responsive or refractory to IV crystalloid fluids.
Severe symptoms; intervention indicated	
Grade 4:	Severe or persistent hypotension is to be managed by the administration of vasopressors. A trial of 25% albumin IV is an additional option, although its efficacy is limited to those with a severe capillary leak. In those who remain with refractory shock in the setting of low filling pressures, high molecular weight starches such as hetastarch (MW 450 kDa) and pentastarch (MW 264 kDa) may be effective in expanding the intravascular volume. Supportive care with invasive and noninvasive ventilation as well as renal replacement may be necessary in severe cases. When available, disease-specific therapy should be initiated as soon as possible to facilitate recovery.
Life-threatening consequences; urgent intervention indicated	During the recovery phase from severe capillary leak, the endothelial injury resolves and the capillary leak becomes less important, resulting in stabilization of blood pressure, at which time fluid overload symptoms and signs may predominate (eg, pulmonary edema, pleural effusions, acute respiratory distress syndrome, systemic edema, ascites). Volume removal with loop diuretics is the first-line therapy in these patients. In those with marginal blood pressure and fluid overload, the combination of loop diuretics and 25% albumin IV may facilitate volume removal. Patients with AKI refractory to diuretics will require renal replacement.

a Information for preparation and storage of SAR444245 is provided in the pharmacy manual.

Abbreviations: AKI= acute kidney injury; CTCAE = Common terminology criteria for adverse events; IV = Intravenous; MW= molecular weight; NCI = National Cancer Institute; VLS= vascular leak syndrome.

6.5.4.7 Dermatologic toxicity

Cetuximab can cause dermatologic toxicities, including acneiform rash, skin drying and fissuring, paronychial inflammation, infectious sequelae (for example, *S. aureus* sepsis, abscess formation, cellulitis, blepharitis, conjunctivitis, keratitis/ulcerative keratitis with decreased visual acuity, cheilitis), and hypertrichosis.

The dosing of cetuximab will be omitted 1 to 2 weeks in the case of severe (Grade 3 or 4) acneiform rash. If acneiform rash improves during this time, then the dose of cetuximab should be reduced as indicated in [Table 12](#). The dose modification guidelines as per the current local label should be followed for dermatologic toxicities other than acneiform rash.

If acneiform rash does not improve during this time, cetuximab will be permanently discontinued.

Participant who have held cetuximab therapy for more than 2 consecutive infusions due to acneiform rash, and upon resolution of the toxicity are still felt to be benefiting from cetuximab treatment may resume cetuximab with Sponsor approval.

Table 12 - Cetuximab dose modification for dermatologic toxicities

Dermatologic toxicities and infectious sequelae (eg, acneiform rash, mucocutaneous disease)	Recommended cetuximab dose modification
1st occurrence; Grade 3 or 4	Day 1 of cycle: delay cycle until condition improves Within cycle: Omit infusion 1 to 2 weeks; if condition improves, continue at the same dose of 250 mg/m². If no improvement, discontinue cetuximab.
2nd occurrence; Grade 3 or 4	Day 1 of cycle: delay cycle until condition improves Within cycle: Omit infusion 1 to 2 weeks; if condition improves, permanently reduce at 200 mg/m ² . If no improvement, discontinue cetuximab.
3rd occurrence; Grade 3 or 4	Day 1 of cycle: delay cycle until condition improves Within cycle: Omit infusion 1 to 2 weeks; if condition improves, permanently reduce at 150 mg/m ² . If no improvement, discontinue cetuximab.
4th occurrence; Grade 3 or 4	Permanently discontinue cetuximab.

6.6 CONTINUED ACCESS TO INTERVENTION AFTER THE END OF THE STUDY

Please refer to the master protocol.

6.7 TREATMENT OF OVERDOSE

Please refer to the master protocol for definition and treatment of SAR444245 overdose.

An overdose of pembrolizumab will be defined as any dose of 1000 mg or greater. There is no specific antidote for overdose with pembrolizumab, or cetuximab. No specific information is available on the treatment of overdose of pembrolizumab. In the event of overdose, the participant should be observed closely for signs of toxicity. Appropriate supportive treatment should be provided if clinically indicated.

6.8 CONCOMITANT THERAPY

Please refer to the master protocol.

7 DISCONTINUATION OF STUDY INTERVENTION AND PARTICIPANT DISCONTINUATION/WITHDRAWAL

7.1 DISCONTINUATION OF STUDY INTERVENTION

Please refer to the master protocol.

7.2 PARTICIPANT DISCONTINUATION/WITHDRAWAL FROM THE STUDY

Please refer to the master protocol.

7.3 LOST TO FOLLOW UP

Please refer to the master protocol.

8 STUDY ASSESSMENTS AND PROCEDURES

[figure not shown]
Please refer to the master protocol and [Section 1.3](#).

8.1 EFFICACY ASSESSMENTS

Please refer to the master protocol.

8.1.1 Assessment of objective response using the most appropriate modality according to the nature of the measurable lesion(s)

Please refer to the master protocol for RECIST 1.1.

8.2 SAFETY ASSESSMENTS

Please refer to the master protocol.

8.3 ADVERSE EVENTS (AES), SERIOUS ADVERSE EVENTS (SAES) AND OTHER SAFETY REPORTING

Please refer to the master protocol.

In addition, combining SAR444245 with other anticancer therapies may increase the frequency and severity of immune-related adverse events related to other anticancer therapies. Immune-mediated endocrinopathies involving the thyroid being the most frequent, T3, T4, TSH, and cortisol level will be monitored for participants in Cohort D1.

8.3.1 Time period and frequency for collecting AE and SAE information.

Please refer to the master protocol for AEs and serious adverse events (SAEs) collection. For participants in Cohort D1 irAEs will be collected until 90 days following last administration of study treatment regardless of whether or not another anticancer therapy is initiated.

8.3.2 Method of detecting AEs and SAEs

Please refer to the master protocol.

8.3.3 Follow-up of AEs and SAEs

Please refer to the master protocol.

8.3.4 Regulatory reporting requirements for SAEs

Please refer to the master protocol.

For pembrolizumab and cetuximab, SAEs that are considered expected will be specified in the reference safety information (country-approved product labeling for pembrolizumab).

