Cycle Day (Visit window in Days)	D-28 to D-1	D1	D8 ^f (±1)	D15 ^f (±1)	D1 (±3)	D8 (±1)	D15 (±1)	30 days (+/- 7 days) after last IMP or at initiation of further therapy	3 months after last IMP admin ±7 days	6 months after last IMP admin ±7 days	Every 3 months after FU Visit 2 ±7 days	Every 3 months +/-14 days		
Pregnancy test	X	X			X			X	X	X			See Section 8.2.5 of the master protocol and Section 10.2 of the master protocol	
Hepatitis serology, CD4 counts and viral load	X ^h	As clinically indicated											See Section 10.2 of the master protocol and Section 10.7 of the master protocol	
Hematology	X	X	X	X	X			X	X				See Section 10.2 of the master protocol	
Coagulation	X	As clinically indicated											See Section 10.2 of the master protocol	
Blood Chemistry	X	X	X	X	X			X	X				See Section 10.2 of the master protocol	

Evaluation ^a	Screening	Treatment Period ^b						End of Treatment	Observation Period ^c			Survival Phone Call Follow-up ^d	Notes	
		Cycle 1			Cycle 2 and beyond ^e			EOT Visit	Follow-Up	Follow-Up	Follow-Up	Phone Call FU		
		Visit 1	Visit 2	Visit 3+										
Cycle Day (Visit window in Days)	D-28 to D-1	D1	D8 ^f (±1)	D15 ^f (±1)	D1 (±3)	D8 (±1)	D15 (±1)	30 days (+/- 7 days) after last IMP or at initiation of further therapy	3 months after last IMP admin ±7 days	6 months after last IMP admin ±7 days	Every 3 months after FU Visit 2 ±7 days	Every 3 months +/-14 days		
Urinalysis ⁱ	X	X			X			X	X				See Section 10.2 of the master protocol	
T3, FT4, TSH & cortisol (Cohort D1 only) ^j	X				X			X	X				See Section 10.2	
Electrolytes (Cohort D2 only)		weekly under treatment and then at the end of treatment, at FU Visit 1 and as clinically indicated												
IMP														
SAR444245		X			X									
Pembrolizumab (Cohort D1 only)		X			X									
Cetuximab (Cohort D2 only)		X	X	X	X	X	X							
Hospitalization ^k		X												
AE/SAE assessment ^l	X	Continuously throughout treatment period						X					See Section 8.3 of the master protocol	
Prior/Concomitant Meds	X	Continuously throughout treatment period											See Section 6.8 of the master protocol	

[figure not shown]
Evaluation ^a	Screening	Treatment Period ^b						End of Treatment	Observation Period ^c			Survival Phone Call Follow-up ^d	Notes	
		Cycle 1			Cycle 2 and beyond ^e			EOT Visit	Follow-Up	Follow-Up	Follow-Up	Phone Call FU		
		Visit 1	Visit 2	Visit 3+										

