Cetuximab can cause dermatologic toxicities, including acneiform rash, skin drying and fissuring, paronychial inflammation, infectious sequelae (for example, *S. aureus* sepsis, abscess formation, cellulitis, blepharitis, conjunctivitis, keratitis/ulcerative keratitis with decreased visual acuity, cheilitis), and hypertrichosis. Acneiform rash occurred in 82% of patients across clinical trials. Grades 3 or 4 acneiform rash occurred in 9.7% of patients. Acneiform rash usually developed within the first two weeks of therapy; the rash lasted more than 28 days after stopping treatment in

most patients. Life-threatening and fatal bullous mucocutaneous disease with blisters, erosions, and skin sloughing, has been observed. It could not be determined whether these mucocutaneous adverse reactions were directly related to EGFR inhibition or to idiosyncratic immune-related effects (eg, Stevens-Johnson syndrome or toxic epidermal necrolysis).

Cetuximab can cause hypomagnesemia which occurred in 55% patients in various clinical trials, including Grades 3 and 4 in 6% to 17%. Hypomagnesemia and accompanying electrolyte abnormalities can occur days to months after initiating treatment. It is recommended to monitor patients weekly during treatment for hypomagnesemia, hypocalcemia, and hypokalemia, and for at least 8 weeks following the completion of treatment and to replete electrolytes as necessary.

Based on animal data and its mechanism of action, cetuximab can cause fetal harm when administered to a pregnant woman. There are no available data for cetuximab exposure in pregnant women. In an animal reproduction study, intravenous administration of cetuximab once weekly to pregnant cynomolgus monkeys resulted in an increased incidence of embryo-lethality and abortion. Disruption or depletion of EGFR in animal models results in impairment of embryo-fetal development including effects on placental, lung, cardiac, skin, and neural development.

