The safety and effectiveness of cetuximab in pediatric patients have not been established. The pharmacokinetics of cetuximab, in combination with irinotecan, were evaluated in pediatric patients with refractory solid tumors in an open-label, single-arm, dose-finding study. Cetuximab was administered once weekly, at doses up to 250 mg/m², to 27 patients ranging from 1 to 12 years old; and in 19 patients ranging from 13 to 18 years old. No new safety signals were identified in pediatric patients. The pharmacokinetics of cetuximab between the two age groups were similar following a single dose of 75 mg/m² and 150 mg/m². The volume of the distribution appears to be independent of dose and approximates the vascular space of 2 L/m² to 3 L/m². Following a single dose of 250 mg/m², the mean AUC0-inf (CV%) was 17.7 mg*h/mL (34%) in the younger age group (1-12 years, n=9) and 13.4 mg*h/mL (38%) in the adolescent group (13-18 years, n=6). The mean half-life of cetuximab was 110 hours (69 to 188 hours) in the younger group and 82 hours (55 to 117 hours) in the adolescent group.

Of the 1662 patients with advanced colorectal cancer who received cetuximab with irinotecan, with FOLFIRI or as monotherapy in six studies, 35% of patients were 65 years of age or older. No overall differences in safety or efficacy were observed between these patients and younger patients.

Please refer to the country-approved cetuximab labeling (eg, USPI, SmPC) for more detailed prescribing information.

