6 STUDY INTERVENTION(S) AND CONCOMITANT THERAPY

6.1 STUDY INTERVENTION(S) ADMINISTERED

Please refer to the master protocol.

For study treatment duration, completion of Cycle 35 is only applicable for Cohort D1.

Dosing sequence for Cohort D1: [REDACTED]

Enrolled participants in Cohort D2 will receive treatment with both SAR444245 and cetuximab until PD.

Dosing sequence for Cohort D2: [REDACTED]

In addition, if a participant has immune unconfirmed progression of disease (iUPD) and is clinically stable, it is at the discretion of the Investigator to continue treating the subject with the assigned treatment per protocol until progression of disease is confirmed (iCPD) at least 4 weeks, but no longer than 8 weeks from the date of the scan suggesting progression of disease (Section 10.9).

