Cardiovascular effects, including QT interval prolongation	
Cetuximab
 
Cardiopulmonary arrest or sudden death have occurred in 2-3% patients with squamous cell carcinoma of the head and neck receiving cetuximab with radiation therapy or a cetuximab product with platinum-based therapy and fluorouracil cetuximab. A history of coronary artery disease, congestive heart failure, or arrhythmias and abnormal serum electrolytes may be predisposing factors.
	
Specifically, for patients receiving cetuximab, exclude patients with electrolytes (magnesium, calcium and potassium) <LLN and monitor serum electrolytes weekly during and for at least 8 weeks after last cetuximab administration.

Immune-mediated Adverse Events	
Pembrolizumab
 
Immune-mediated adverse events are designated as important identified risk for pembrolizumab.
 
Cetuximab
 
Not reported as such in the SmPC.
	
Dose modification and treatment guidelines for immune-related reactions are provided in Table 9.
 
Patients treated with cetuximab:
 
If a diagnosis of ulcerative keratitis is confirmed, treatment with cetuximab should be

Potential risk of clinical significance	Summary of data/rationale for risk	Mitigation strategy
	
Patients presenting with signs and symptoms suggestive of keratitis such as acute or worsening: eye inflammation, lacrimation, light sensitivity, blurred vision, eye pain and/or red eye should be referred promptly to an ophthalmology specialist.
 
Very rarely, Stevens-Johnson syndrome/toxic epidermal necrolysis may occur in patients treated with cetuximab.
	
interrupted or discontinued. If keratitis is diagnosed, the benefits and risks of continuing treatment should be carefully considered. Cetuximab should be used with caution in patients with a history of keratitis, ulcerative keratitis or severe dry eye. Contact lens use is also a risk factor for keratitis and ulceration.

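### In substudy 04, expectedness of cetuximab-related SAEs is tied to the pembrolizumab label, although Cohort D2 receives no pembrolizumab

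*Protocol*

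**What the plan says.** Section 8.3.4 of substudy 04 first defers to the master protocol and then adds one sentence of its own, for pembrolizumab and cetuximab together: "SAEs that are considered expected will be specified in the reference safety information (country-approved product labeling for pembrolizumab". The subject is two products; the bracket names one label.

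Elsewhere the substudy keeps the two products apart. The schedule of activities (Section 1.3) lists "Pembrolizumab (Cohort D1 only" and, separately, "Cetuximab (Cohort D2 only". Section 6.1 confirms the D2 regimen: "Enrolled participants in Cohort D2 will receive treatment with both SAR444245 and cetuximab until PD".

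Cetuximab labelling is cited in three other places in substudy 04. Section 2.3.1.2 says "Please refer to the country-approved cetuximab labeling", for prescribing detail. Table 15 (Section 10.11) points to it for treating infusion reactions. Section 6.5.4.7 points to the local label for skin toxicities other than acneiform rash. None of these concerns the expectedness of SAEs.

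**The concern.** Expectedness is judged product by product, against the reference safety information of the product to which the event is attributed. Section 8.3.4 covers cetuximab but gives it no reference of its own. Unlike the background text on risks, this is the section that sites and safety staff apply when they report an SAE.

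At stake is the expedited-reporting classification of cetuximab-related SAEs in Cohort D2. If the wrong label is consulted, two errors are possible. An event listed for pembrolizumab but not for cetuximab could be called expected and might not be expedited. An event well known for cetuximab but not listed for pembrolizumab could be called unexpected and reported needlessly. The first error is the more serious one.

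**Working it through.** The plan gives no figure on this point and no arithmetic applies. The check sets the relevant sections side by side.

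1. **Who receives what.** Sections 1.3 and 6.1 of substudy 04: D1 receives SAR444245 plus pembrolizumab; D2 receives SAR444245 plus cetuximab. No D2 participant is scheduled for pembrolizumab.

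2. **Which label the rule names.** Section 8.3.4 covers both partner drugs and names the pembrolizumab label only. For D1 the drug and the label match. For D2 they do not.

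3. **Whether another section supplies the missing reference.** The citations in Sections 2.3.1.2, 6.5.4.7 and 10.11 show that a country-approved cetuximab label is available and in use, but for prescribing, dose modification and treatment of reactions. None designates it as reference safety information.

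4. **Where the wording probably came from.** Section 8.3.4 of the gastric substudy (Cohorts B1 to B3) and of the hepatocellular substudy (Cohort C) carries the same sentence with pembrolizumab as its only subject. There rule and label agree. In substudy 04 cetuximab appears in the first half of the sentence without a matching change in the bracket. The sentence is complete as printed, so redaction or text extraction does not explain it.

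5. **Whether the choice of label matters.** Table 15 of substudy 04 compares the two products:

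| Risk | Pembrolizumab | Cetuximab | Possible error under the literal rule |
|---|---|---|---|
| Nephrotoxicity | Nephritis and acute kidney injury common | Not reported in the SmPC | Cetuximab-attributed event called expected |
| Hypomagnesaemia | No entry | Very common | Cetuximab-attributed event called unexpected |

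The profiles therefore differ in both directions on the protocol's own account.

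6. **How many SAEs are affected.** This would need the number of SAEs attributed to cetuximab in D2 and the share of them on which the two labels disagree. The documents give neither.

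**The case against.** The strongest reply is that this is an incomplete edit with little practical effect. Safety staff would see the slip and use the cetuximab label, and the master protocol, to which Section 8.3.4 first defers, may already name one. The master protocol is not in the part of the document available here, so that cannot be excluded. It would not cure the sentence, though: the substudy text is explicit and would then conflict with the master protocol.

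Three stronger readings are tempting, and the objection defeats each of them.

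- *All SAEs in D2 are judged against the wrong label.* A reader might infer this, but the sentence covers only pembrolizumab and cetuximab. Every D2 participant also receives SAR444245, whose expectedness is left to the master protocol.

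- *Expedited reports of immune events will be suppressed.* Table 15 does say of immune-mediated events with cetuximab "Not reported as such in the SmPC". The same row, however, goes on to describe keratitis and, very rarely, Stevens-Johnson syndrome or toxic epidermal necrolysis with cetuximab, so it is not a clean contrast. Section 2.3.1.3 also anticipates more immune-activation events with SAR444245 combinations, so such an event would naturally be assessed against SAR444245 as well.

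- *The number of misclassified SAEs can be estimated from published rates.* Section 2.3.1.2 says "Grades 3 or 4 acneiform rash occurred in 9.7% of patients", and one could multiply such rates by 40. But grade measures severity, not seriousness, and the rates come from other trials. D2 excludes participants with abnormal magnesium, calcium or potassium (Section 5.2), and Section 2.2.3 describes its population as post-cetuximab. Whether a given event is absent from the pembrolizumab label cannot be settled without that label; Section 2.3.1.1 lists immune-related skin reactions for pembrolizumab, so even a serious rash is not a clear case.

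What stands of the objection is its limit on scope and size. What does not stand is the idea that a reporting rule may rely on its readers to disregard its wording.

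**Conclusion.** The point holds as an internal inconsistency in an operative safety-reporting rule. Taken literally, Section 8.3.4 of substudy 04 has cetuximab-related SAEs in Cohort D2 assessed for expectedness against the label of a drug that cohort does not receive. Some could be misclassified in either direction.

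The reach is limited to cetuximab-related SAEs among about 40 planned D2 participants (Section 9.2). The number affected is unknown and may be small or zero. The conclusion assumes that the sentence is applied as written and that the master protocol does not override it. The primary endpoint, the sample size and the efficacy analysis are untouched. It should be corrected, but it does not threaten the trial's results.

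**What to change.** In Section 8.3.4 of substudy 04, change the bracket so that it names the country-approved product labelling of each product: pembrolizumab for Cohort D1 and cetuximab for Cohort D2. Check the new wording against Section 2.3.1.2, which already cites the cetuximab label, and against whatever the master protocol names as reference safety information.

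The cost is one phrase at the next amendment. No dose, schedule, assessment or analysis changes.
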